
intervention effects vary among subgroups. Those with significant interactions ($p < .15$) will be considered as candidates for identifying subpopulations.

Cost

We will calculate the incremental cost per quit of the interventions over the 6-month follow-up period as follows: (total per-person costs of LCS-tailored intervention – total per-person costs of the lowest intensity comparator)/(cessation rate with the LCS-tailored intervention – cessation rate with the lowest intensity comparator).⁹⁶ From these comparisons, we will also be able to construct a “league table” comparing the relative cost-effectiveness of different intervention components.⁹⁷ While the study is specifically powered to detect differences across factorial dimensions, we will develop incremental cost per quit estimates for all intervention comparisons that are proven effective, whether it be for individual factorial dimensions’ main effects (counseling duration, NRT duration, or systematic referral), for specific permutations of the intervention components versus usual care or for intervention permutations versus each other. Costs of implementation included in our analyses will be: 1) personnel time related to intervention delivery (training, minutes of counseling, contact attempts, maintaining data and information systems), 2) NRT costs (medication, delivery), and 3) systematic referral to community resources. While systematic referral is free in Boston, access to similar services elsewhere in the country may not be, so this will be an element of our sensitivity analyses. We will also include patient time as an indirect cost. The TTS database will document all implementation costs. All intervention costs incurred will be included in the analysis, even for patients who do not complete their intervention course. Research costs will be excluded. The denominator for the cost analyses will be based on the primary outcome. Uncertainty in cost and effectiveness inputs will be incorporated into the incremental cost per quit comparisons using Monte Carlo methods allowing us to determine whether these ratios are significantly different from zero. The robustness of the cost-effectiveness ratio estimates will be further examined in sensitivity analyses in which each parameter is varied, singly and in combination, through plausible ranges. Sensitivity analyses will also consider how cost-effectiveness changes based on payment arrangements and stakeholder (provider, payer, and patient) perspectives to identify where incentives to adopt the interventions differ. For example, overhead costs such as counseling training and data/information systems are borne by the provider, and indirect costs are borne by patients, but treatment costs (counseling, NRT) and the cost of systematic referral-style resources may be borne by providers, payers, and/or patients (e.g., copayments). Assessing how assignment of costs to different stakeholders changes cost-effectiveness from different perspectives will be critical to understanding how to scale up the intervention to other LDCT screening settings and what payment policies will produce the best public health outcomes.

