
Sample size/ Power calculations

Power calculations are based on our primary analysis, which is to assess the effect of each intervention component (e.g., shorter counseling vs. longer counseling) on our primary outcome, 7-day point-prevalence tobacco abstinence at 6-month follow-up. This is a two-sample comparison between patients that receive one intervention component (e.g., longer counseling) and those that receive the other (e.g., shorter counseling). We conservatively estimate that 160 patients/month will have LCS, of whom 50% will be current smokers. Assuming a 50% enrollment rate, we aim to recruit a total N of 720 patients. This sample size allows us to allocate N=360 to each treatment component comparison (main effect). Our

Reference rate	Relative Risk		
	1.4	1.45	1.5
16%	0.71	0.80	0.87
17%	0.74	0.83	0.90
18%	0.77	0.86	0.92
19%	0.80	0.88	0.93
20%	0.83	0.90	0.95
21%	0.85	0.92	0.96
22%	0.87	0.93	0.97

outcome of interest will also be assessed at 3-month followup, which allows us to use a longitudinal generalized estimating equations approach wherein power is proportional to the within-person correlation. We estimate the correlation between 3 month and 6 month smoking cessation to be 0.6. Assuming N=360 patients in each condition, a Type 1 error rate of 0.05, a 25% attrition rate by 6 month follow-up, and a 15% cessation rate for the reference group, we will have 92.3% power to detect a risk ratio of 1.6 (15% vs. 21%). Under those same conditions, but with a 10% cessation rate for the reference group, we will have 79.0% power to detect a risk ratio of 1.6 (10% vs. 16%). Given that this is full factorial design, we will have the same power to detect two-way interactions between components. Further, we will also have 77.9% power to detect a risk ratio of 2.0 in the difference between our most intensive set of treatments (longer counseling, longer NRT, and community support; N=90) and our least intensive set of treatments (shorter counseling, shorter NRT, and no community support; N=90) after six months, assuming a 15% reference rate and 25% attrition.

Reduction from initial power calculations

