This study was initially powered conservatively to detect a smaller risk ratio of 1.4 and did not account for additional power provided through within-person correlation via repeated measurement of our outcome of interest. Initial power calculations, assuming a Type 1 error rate of 0.05, 25% attrition at 6 months, and no within-person correlation showed that our original N of 960 patients (N=480 per condition) gave us 85.0% power to detect a risk ratio of 1.4 with a reference rate of 15%. Updated power calculations accounting for within-person correlation of 0.6 show that this original N gives us 96.8% power to detect our target risk ratio of 1.6, assuming 25% attrition at 6 months and a 15% reference cessation rate.

Our previous power calculation assumed a 25% attrition rate at 6 months. We re-examined this assumption after halfway through the recruitment. Our new estimates are 12.7% attrition rate at 3 months and 15.9% attrition rate at 6 months. Based on these estimates, we further reduce the target recruitment from 720 to 640. Combining data from both 3-month (estimated N=559) and 6-month (estimated N=539) assessments, the effective sample size will be 768 after taking into account of within-person correlation using a conservative estimate of 0.6. The new sample size will have 70% power to detect a risk ratio of 1.6 (10% vs. 16%) and 81% power to detect a risk ratio of 1.7 (10% vs. 17%).

VII.. RISKS AND DISCOMFORTS (Stratify by common and uncommon)

Prior to enrollment, potential patients will be cautioned about the potential negative psychological and physical implications of joining the study and/or quitting smoking.

Psychological Risks

Individuals may find it stressful to answer questions and discuss their smoking behaviors. The risks associated with these discussions are minimal, especially when compared to the benefits of smoking cessation.

The potential risks to subjects include: 1) speaking with a counselor about smoking and/or cancer-related topics has the potential for increasing psychological vulnerability; 2) experiencing physical and emotional withdrawal symptoms from smoking cessation; and 3) potential side effects of using nicotine replacement therapy.

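### The Cost section ties cost-per-quit estimates to an undefined finding of effectiveness; read as significance, this makes the reported ratios too low on average and leaves other components without one

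*Combined protocol and SAP*

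**What the plan says.** The Cost part of section VI (Biostatistical Analysis) opens without a condition: "We will calculate the incremental cost per quit of the interventions over the 6-month follow-up period as follows". The formula divides the difference in per-person cost by the difference in cessation rate, each against the lowest intensity comparator. From these comparisons a league table is to be built, "comparing the relative cost-effectiveness of different intervention components".

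The next sentence adds a condition: "we will develop incremental cost per quit estimates for all intervention comparisons that are proven effective". It names the main effects of counseling duration, NRT duration and referral, and also comparisons involving particular combinations of components. No test, significance level or time point defines the condition. Nothing says what is reported for a component that does not meet it.

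The effect measure is fixed: "The denominator for the cost analyses will be based on the primary outcome", that is, abstinence at 6 months. On uncertainty the section says: "Uncertainty in cost and effectiveness inputs will be incorporated into the incremental cost per quit comparisons using Monte Carlo methods". One-way and multi-way sensitivity analyses follow.

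**The concern.** If a ratio is produced only when the quit difference is significant, that difference does two jobs: it passes the filter and it supplies the denominator. Significant differences exceed the true difference on average, so the cost per quit built on them is on average too low. The Monte Carlo and sensitivity analyses act on ratios that have already been selected and are not described as correcting for this.

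The second consequence is omission. A cheap component can be good value with a modest effect. The Cost section itself says that referral carries no charge in Boston, so referral is the obvious candidate to be left without an estimate. The section expects the results to inform scale-up and payment policy, where both faults would matter.

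**Working it through.** **Inputs**
- Significance level: the Sample size/Power section gives "a Type 1 error rate of 0.05". Sidedness is not stated; two-sided is assumed.
- Rates: 10% vs 16% and 10% vs 17% (Reduction from initial power calculations); 15% vs 21% and a risk ratio of 2.0 on 15% (Sample size/Power). The plan labels 15% vs 21% a risk ratio of 1.6, but 21/15 = 1.4, and 1.6 × 15% = 24%. Both are run.
- Numbers per level: 640/2 = 320. Patients lost to follow-up count as smokers, so all 640 enter the 6-month test. The plan's effective sample size of 768 gives 384 per level, taken as stated. Each cell has 640/8 = 80.
- Incremental cost is held fixed, an assumption, because the documents give no cost figures.

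**Step 1: reproduce the plan's power.** With p̄ the mean of the two rates,

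power = Φ{ [(p2 − p1) − 1.96 √(2p̄(1 − p̄)/n)] / √([p1(1 − p1) + p2(1 − p2)]/n) }.

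For n = 384 and 10% vs 16%: (0.06 − 1.96 × 0.02427)/0.02417 = 0.514, so power = 0.696. For 10% vs 17% it is 0.811. These match the plan's 70% and 81%. At 320 per level the same formula gives 0.617 and 0.737.

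**Step 2: apply the filter.** For each scenario 2,000,000 binomial trials were simulated. Only those whose pooled z-test favoured the more intensive level at two-sided 0.05 were kept.
- Inflation factor = mean kept difference / true difference.
- Relative cost per quit = mean over kept trials of (true difference / observed difference).

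Example, 10% vs 16% at 320 per level: the mean kept difference is 7.61 points, and 7.61/6.00 = 1.27. Mean relative cost per quit is 0.83. It is not 1/1.27 = 0.79, because the mean of a reciprocal exceeds the reciprocal of the mean.

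| Scenario | n per group | Power (simulated) | Inflation factor | Mean cost per quit / truth |
|---|---|---|---|---|
| 10% vs 16% | 320 | 62% | 1.27 | 0.83 |
| 10% vs 16% | 384 | 70% | 1.20 | 0.88 |
| 10% vs 17% | 320 | 74% | 1.17 | 0.91 |
| 10% vs 17% | 384 | 82% | 1.11 | 0.95 |
| 15% vs 21% | 320 | 51% | 1.40 | 0.75 |
| 15% vs 24% | 320 | 82% | 1.11 | 0.96 |
| 10% vs 14% (assumed) | 320 | 34% | 1.68 | 0.62 |
| 10% vs 13% (assumed) | 320 | 22% | 2.13 | 0.49 |
| 15% vs 30%, single cells | 80 | 63% | 1.26 | 0.84 |
| 15% vs 24%, single cells | 80 | 30% | 1.80 | 0.58 |

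Without the filter, the mean difference equals the true difference in every row.

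**Step 3: how regular is the bias?** At 10% vs 16%, 78% of kept trials overstate the effect at 320 per level and 68% at 384. So 22% to 32% do not.

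**Step 4: a different filter.** The plan also has a GEE over 3 and 6 months. If that decides effectiveness while the denominator stays at 6 months, the factor at 10% vs 16% is 1.18 (320 per level, correlation 0.6, equal rates at both times, no dropout).

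**Step 5: omitted components.** Suppose all three components truly achieve 10% vs 16% and the tests are treated as independent. The chance that at least one misses is 1 − 0.70³ = 0.66 at 70% power and 1 − 0.62³ = 0.76 at 62%.

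**The case against.** The strongest reply is that the plan does not restrict itself. The word *only* is absent, and the section opens with an unconditional formula and league table. The conditional sentence can be read as extending the analysis to combinations of components where those prove effective. The plan also intends to ask by Monte Carlo whether the ratios differ from zero, a step that would be largely redundant if every ratio had already passed a significance test. Quit differences for all three components are planned in the primary analysis, so effect estimates would exist whatever the p-value. And a ratio is unstable when its denominator is near zero, which is a fair reason to hesitate over ineffective comparisons.

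Much of this stands. A reader might infer that cost per quit will certainly be limited to significant comparisons, or that the league table will certainly be biased and truncated. The text does not establish either. It supports an unconditional and a conditional analysis within one paragraph, and significance as the meaning of the condition is an inference. Nor does the text say that the test deciding effectiveness is the 6-month test; with the GEE the inflation is smaller, though still present.

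Two things are not answered. The conditional sentence names the three main effects, so it cannot be confined to combinations. And an undefined condition leaves the choice of reported ratios until results are known. Instability of a ratio calls for showing its uncertainty, not for leaving the comparison out.

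**Conclusion.** The point holds as an ambiguity with a material consequence if the conditional sentence is followed on its natural reading. At the two rate pairs behind the final sample size (10% vs 16% and 10% vs 17%), mean cost per quit among significant results is 0.83 to 0.95 of the truth. At the printed 15% vs 21% it is about 0.75; at a true risk ratio of 1.6 on 15% it is 0.96. The lower figures, 0.62 and 0.49, rest on quit rates of 14% and 13% that the documents do not give. They show direction and range, not the expected size.

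A reader might also infer that every reported ratio will be too low. That does not follow: the bias is an average over repeated trials. All figures assume a two-sided 0.05 filter and a fixed incremental cost. The issue concerns a secondary economic analysis and leaves the primary effect estimates untouched, but it is worth correcting before analysis.

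**What to change.** For the three main effects, delete the condition. State that incremental cost and incremental quits will be reported for all three components whatever the p-value, with their joint uncertainty from the Monte Carlo analysis already planned. Give the ratio beside them, marked as imprecise or dominated where the quit difference is near zero or negative. Removing the filter removes selection bias from the quit difference; it does not stabilise the ratio, which is why cost and quits should be shown separately. Treat comparisons between single cells (80 per cell) as exploratory. If a condition is kept for those, define its test, level and time point in advance.

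The cost is a little more analysis of data already collected: the plan records all implementation costs, including those for patients who do not finish their intervention. The downside is that some ratios will be very imprecise and the league table less tidy.

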Recruitment Point 2 Pre-COVID: LDCT Exam. In March 2020 due to the COVID pandemic we stopped all ipad use in the clinics. RP2 procedures from April 2019-March 2020 are described below: All patients who arrive for LDCT screening will be given an iPad from front desk staff to facilitate study enrollment. The iPad will have a live data feed from the study's database, allowing it to determine if the patient is already in the study or has refused further contact. If the patient had already enrolled in the study at Point 1, the iPad will play a short video message reinforcing the importance of continuing with the program and study. If patients have consented to the study but have not completed the baseline survey, the iPad will play a short video message reminding them to complete the survey and offer them the opportunity to have the survey resent to them. If the patient had not enrolled at Point 1 and had permitted further contact, the iPad will present questions in the form of a REDCap survey to identify patient eligibility for the study. Eligible patients will then receive a short video recruiting them to the study, and will inform them that they will be contacted soon after the screening test by an RA who will explain the study and offer participation. After leaving the LDCT facility, eligible patients will be contacted by the RA who will use the same workflow as described at Point 1 (i.e., screen, consent, administer baseline survey). If the patient is ineligible for the study, the iPad will play a short video encouraging smoking cessation. If patients arriving for the LDCT test had refused further contact at Point 1, they will receive brief advice to quit, representing usual care, via the iPad but no contact about the study.

We will develop a live data feed on a secure Partners server to be used for patient tracking, real time randomization, and all data entry. Password protected iPads will communicate over the secure wireless network with the SQL database.

We will be providing \$5 coffee cards to staff at the study sites for their assistance with the study.

Recruitment Point 2 Post COVID: LDCT Exam After leaving the LDCT facility, eligible patients will be contacted by the RA who will use the same workflow as described at Point 1 (i.e., screen, consent, administer baseline survey)

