Recruitment Point 3. LDCT Result. After the patient has received the result, patients who have not previously enrolled or refused further contacts will be sent a short video recruitment message tailored to the result via a secure, encrypted email including a secure REDCap survey link, or a letter with a URL to a secure REDCap survey. It will invite them to join the study, and

give brief cessation advice from [name] or [name]. Patients will then be contacted by the RA who will use the same workflow as described for Point 1 (i.e., screen, consent, administer baseline survey). Patients who enrolled at an earlier point will receive a short video embedded in a secure REDCap survey tailored to their test result to address why quitting and study participation remain important.

Hispanic/Latino patients that do not enroll will have MRNs shared with study investigators to be approached for protocol # 2019P002549.

Patients may also be contacted for research purposes from the team in the future.

Recruitment Summary: Our recruitment strategy is designed to require little additional effort at busy radiology sites, but make systematic and repeated recruitment offers to enable us to achieve maximal reach.^{5,50,54,55,56,59} To provide data for our implementation evaluation (Aim 3), we will record the numbers and characteristics of patients who are identified, eligible, and enrolled at each time point. We will document reasons for ineligibility and refusal and document EHR-recorded sociodemographic and biological characteristics, medical history, and cancer history of refusers.

Randomization. Patients will be randomized at the time of enrollment (i.e., completed consent and baseline survey), stratified into 9 randomization strata (3 groups of LCS study sites and 3 recruitment points), to a LCS-tailored intervention treatment arm. The intervention arms will consist of 8 groups of equal proportions, based on a 3-factor fully crossed factorial design to efficiently test components that vary on counseling duration, NRT duration, and provision of systematic referral.

V. STUDY PROCEDURES

Data management. A centralized SQL database will be used for patient identification and recruitment, randomization, patient tracking, and data input. It will interface with all data collection efforts (RAs will enter in REDCap).

Intervention arm components

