We will develop 8 versions of the multi-component intervention that differ in 3 critical treatment factors: duration of counseling contact (4 vs. 8 sessions), duration of free NRT (2 vs. 8 weeks), and offer of systemic referral to community based resources.⁵⁰

(1) Counseling. Previous interventions conducted by the PIs are the basis for the personalized, algorithm-driven protocol for the short intervention; the longer intervention will be modified from Project CLIQ⁵⁰ and [name] tobacco treatment trial with cancer patients.⁶¹ Patients randomized to the short and long duration counseling conditions will be offered 4 sessions. Those assigned to the long duration counseling will also be offered 4 additional sessions.

Tobacco Counseling Content. As in Project CLIQ and Reach, counseling sessions will be protocolized according to the 5As format for smoking cessation.⁵ Counseling will incorporate patients' risk perceptions before and after the LCS results. The risk counseling content⁶³ emphasizes understanding the personal implications of risk beliefs and aims to reduce cognitive

biases (protective benefits of a negative screen). The counseling protocol elicits 1) contrasts between personal and comparative risk, 2) reasons underlying perceived risk, and 3) beliefs about the connections between risk, smoking, and lung cancer. Counselors will: 1) assess preferences for health information/numeracy; 2) explore the personal meaning of risk; 3) personalize negative and positive risk frames (need to quit, benefits of doing so); 4) emphasize personal magnitude of risk reduction; and 5) acknowledge ambivalence. The TTS will use Motivational Interviewing (MI) an empathic and supportive treatment style,⁶⁴ that can deliver personalized risk counseling, enhance motivation for behavior change, and is effective for patients not ready to quit⁶⁵ and medically and socio-economically vulnerable smokers MI is well suited for LCS patients because: 1) MI focuses on building self-confidence and resolving ambivalence; 2) MI tools (i.e., open-ended questions, affirmations, reflections, and summarizing statements) are effective when addressing sensitive topics; and 3) MI's strategy is effective when communicating about risk.⁶⁴ Undergoing LCS might increase or decrease smokers' risk perceptions, motivation to quit, and cessation efforts.^{18,41, 44, 67, 68}

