Proximal Outcomes/Mediators

All proximal outcomes/mediators will be assessed via survey at baseline and follow-up. Smoking beliefs. Readiness to quit (1 item 10-point 'contemplation ladder' ^{84,85}), importance and confidence to quit (1 item 10-point scales), 4 item perceived lung cancer risk, and 2 item perceived benefits of quitting.^{47,57} Health and screening beliefs. Self-reported overall health status (1 item from the SF-36 survey⁸⁶), 2 item perceived benefits of screening.^{47,57} Emotional symptoms. Anxiety and depression symptoms (PROMIS Anxiety and Depression 4a short-forms), worry about lung cancer (1 item about level^{87, 88}). Environmental factors. Living with a smoker in the household, 1 item 4-point scale about rules about smoking in the household⁸⁹, environmental workplace/hobby exposure and social support (PROMIS emotional and informational 4a short forms).⁸⁸

Analysis plan

All analyses will be intent-to-treat; we will classify patients who are lost to follow-up and those who do not provide a sample as current smokers.⁹² We will explore whether the mechanism of missing data is missing at random by comparing patient characteristics between those who complete follow-up vs. those who do not. We will perform sensitivity analysis: 1) limited to those who have complete data, and 2) multiple imputation for missing data.⁹³

Factorial design

In a factorial research design, two or more independent variables are concurrently examined within the same trial.^{94, 95} The three proposed factors will be crossed with one another to create a total of eight experimental conditions. An equal number of subjects will be randomly assigned to each condition, using a random number generator. This is not an 8-arm randomized controlled trial, but instead allows for an efficient examination of main effects for each variable over the entire sample of 640 subjects. This approach allows examination of three key treatment development questions in a much more time-efficient and economical manner by simultaneously performing three studies within the single trial. This achieves power to detect between-group differences that is equivalent to performing three separate randomized trials.⁹⁴

Outcomes/analysis

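### The Cost section promises cost per quit against usual care, but every randomised condition is active treatment and no usual-care data or source is planned

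*Combined protocol and SAP*

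**What the plan says.** Section VI, Cost, defines incremental cost per quit as a difference in per-person cost divided by a difference in cessation rate. The comparator in the numerator is "total per-person costs of the lowest intensity comparator" and in the denominator "cessation rate with the lowest intensity comparator".

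Two sentences later the section widens the scope: "we will develop incremental cost per quit estimates for all intervention comparisons that are proven effective". It then lists three kinds of comparison: main effects of the three factors, estimates "for specific permutations of the intervention components versus usual care", and permutations compared with each other. The cost denominator is to rest on the primary outcome, which is 7-day abstinence at 6 months.

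On the design, Section IV, Randomization, states: "The intervention arms will consist of 8 groups of equal proportions, based on a 3-factor fully crossed factorial design". Section VI, Factorial design, says the same: "The three proposed factors will be crossed with one another to create a total of eight experimental conditions". On the minimum treatment, Section V, Intervention arm components, states: "Patients randomized to the short and long duration counseling conditions will be offered 4 sessions". The short NRT arm receives one 2-week kit.

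The protocol says what usual care consists of in one place only. Section IV, Recruitment Point 2 Pre-COVID, says of patients who had earlier refused further contact that "they will receive brief advice to quit, representing usual care", delivered by iPad.

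**The concern.** The listed usual-care comparison has no arm behind it. A cost-per-quit ratio needs a cost and a 6-month quit rate for each side. The plan provides neither for usual care and does not say where they would come from.

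Two things are at stake. First, if the comparison is attempted, its source would be chosen after the trial results are known, and the estimate could appear beside randomised ones without being marked as different in kind. Second, if the lowest-intensity condition is used and reported as usual care, readers would take an active programme for routine practice. The Cost section says its perspective analyses are meant to inform scale-up to other screening settings and payment policy. For that purpose the difference between adding to an existing programme and starting one matters.

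**Working it through.** The plan states no figure for this comparison, so there is none to reproduce. The check is whether any planned data can fill the two sides of the ratio.

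**1. Count the randomised conditions.** Three two-level factors fully crossed give 2 × 2 × 2 = 8 conditions. With the current target of 640 (Section VI, Outcomes/analysis), 640 / 8 = 80 per condition, and 8 × 80 = 640. The 90 per condition in the power section matches the former target: 720 / 8 = 90. In both cases the eight conditions use the whole sample, so 0 patients are randomised to anything else.

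**2. Find the minimum treatment.** The least intensive condition is short counselling, short NRT and no referral. From Section V, its patients are offered 4 counselling sessions and, absent a contraindication, one free 2-week patch kit. That is active treatment. It does not match the brief iPad advice that Section IV describes as usual care.

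**3. Look for usual-care data outside the randomised sample.**

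| Needed for the ratio | What the plan provides |
|---|---|
| 6-month abstinence under usual care | None planned. The 3- and 6-month assessments are timed from enrolment. For refusers, Section IV, Recruitment Summary, records reasons for refusal and EHR characteristics and history. |
| Cost under usual care | None planned. Implementation costs come from the tobacco treatment specialists' database, which covers intervention delivery. |
| An external quit rate or cost | No source named. |
| The usual-care procedure itself | iPad use in clinics stopped in March 2020. |

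**4. Apply the section's own condition.** Estimates are limited to comparisons shown to be effective. With no usual-care group, the trial cannot show any permutation effective against usual care, so its own data cannot meet the condition for this comparison.

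**5. See what substituting the lowest-intensity condition would change.** Write c for per-person cost and q for quit rate, with X a permutation, L the lowest-intensity condition and U usual care.

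- Stated formula: (cX − cL) / (qX − qL).
- Against usual care: (cX − cU) / (qX − qU) = [(cX − cL) + (cL − cU)] / [(qX − qL) + (qL − qU)].

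The trial estimates the first term in each bracket. It gives no information on the second terms, cL − cU and qL − qU, which are the cost and effect of the shared base package. The numerator and denominator both change, so the documents do not show whether the ratio against usual care would be larger or smaller than the ratio against L. The two ratios answer different questions, and one cannot stand in for the other.

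**The case against.** The strongest reply is that the words are loose or left over, and that the lowest-intensity condition is meant. The only formula in the section names that comparator, and usual care appears just once there. This may well be right. On that reading the clash with the formula disappears, but the label still conflicts with Section IV and describes an active arm as usual care. The same wording change is needed.

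A second reply is that the effectiveness condition makes the promise harmless: nothing can be shown effective against usual care, so no estimate is triggered. This does limit the likely harm, and the most probable result on a strict reading is no estimate at all. The plan would still list an analysis that cannot be done.

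A third is that the planned Monte Carlo and sensitivity analyses could accommodate a usual-care scenario. They could, but they propagate uncertainty around inputs, and no usual-care input is specified.

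Three stronger readings are tempting, and the documents support none of them:

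- A reader might infer that volunteers will be compared with refusers, giving a confounded estimate. No section proposes this, no cessation outcome is planned for refusers, and the iPad advice ended in March 2020.
- A reader might infer that the plan claims effectiveness over usual care. Aim 2, the factorial section, the primary analysis and the power section all define effects as contrasts between randomised components or conditions.
- A reader might infer that the cost analysis as a whole is unsound. The main-effect and permutation-versus-permutation comparisons in the same sentence are randomised and stand.

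**Conclusion.** The comparison with usual care is wrong as written. It cannot be estimated from the trial, cannot meet the section's own effectiveness condition, and is inconsistent with the comparator in the stated formula. In size, 0 of 8 conditions and 0 of 640 randomised patients are usual care. The effect on any cost-per-quit figure cannot be computed, because the documents give no usual-care cost or quit rate.

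The defect is confined to one of three types of cost comparison. Cost is not named in any of the three Specific Aims, and the primary factorial analysis, sample size and error rate are untouched. The correction is small but worth making.

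The conclusion assumes that usual care means what Section IV describes, or at least something less than 4 offered sessions plus free NRT. If the authors mean the lowest-intensity condition, the point becomes one of labelling, with the same remedy.

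**What to change.** In Section VI, Cost, replace the usual-care wording with *versus the lowest intensity condition (short counselling, short NRT, no referral)*. Keep the main-effect comparisons and the comparisons of permutations with each other; the lowest-intensity condition should not become the only reference. Add one sentence stating that the trial gives no randomised estimate of cost per quit against usual care.

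If a usual-care scenario is wanted, specify in advance the external source for its quit rate and cost, label the result as modelled and non-randomised, and carry the uncertainty of those inputs into the Monte Carlo analysis.

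The basic change is a rewording plus one sentence. It needs no new data and costs no power. The downside is one fewer cost comparison. The optional scenario adds the work of finding and justifying the external inputs.
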